11.1.3 Visit 3: Week 2 (Day 14 ± 3 Days) Visit

The following procedures will be conducted at this visit (if a subject terminates early, all final visit [Week 12/Final Visit] procedures must be performed):

- 1. The evaluator will perform the efficacy evaluations including the EGSS, inflammatory and non-inflammatory lesion counts. The EGSS is performed prior to the lesion counting. Every effort should be made for the same qualified and validated evaluator to perform the efficacy evaluations at all visits from Baseline to Week 12 for the same subject.
- 2. For subjects who are applying study drug to truncal acne, the TSS will be performed. Note: lesion counts will not be performed for truncal acne.
- 3. The evaluator will perform the Cutaneous Safety and Tolerability Evaluations. For subjects who are applying study drug to truncal acne, then the Cutaneous Safety and Tolerability Evaluations will also be performed for these areas.
- 4. Record changes in any concomitant medications / therapies since the previous visit under Prior and Concomitant Medications or Therapies. Check for prior and concomitant medications / therapies as per Section 9.4.
- 5. Record any new AEs reported spontaneously by the subject or changes in any ongoing AEs.
- 6. Perform a urine pregnancy test for all females who are premenses and FOCBP. The urine pregnancy tests will be supplied by the CRO/designee.
- 7. The study coordinator or designee will retrieve and weigh the used study drug pump. Record the weight of the pump (with the cap on) to the nearest 0.1 g. Note: a new pump

will **NOT** be dispensed at this visit. The original pump will be re-dispensed back to the subject.

- 8. The study diary calendar will be collected and reviewed for compliance. Any missed doses or deviations should be reported. A new study diary calendar will be dispensed.
- 9. The study coordinator or designee will remind the subject of the proper technique for application of study drug (Section 10.1.3). At this visit, the subject will apply the study drug at the study center under the direction of the study coordinator or designee to confirm proper technique. Any necessary retraining can be completed. The study drug should be applied **after** all clinical assessments. The study coordinator or designee will remind the subjects to apply the study drug once daily at home in the evening up to the evening prior to the Week 12 visit (study drug will not be applied in the evening after this study visit).
- 10. The study coordinator will instruct the subject to use a Sponsor/investigator-approved, non-medicated sunscreen of at least SPF 15, and to wear protective clothing during the day (eg, a hat) if exposure cannot be avoided.
- 11. Schedule the next study visit at Week 4 (Day 28 ± 3 days). Remind the subject to not apply study drug on day of next study visit, prior to the clinic visit.

11.1.4 Visit 4: Week 4 (Day 28 ± 3 Days) Visit

The following procedures will be conducted at this visit (if a subject terminates early, all final visit [Week 12/Final Visit] procedures must be performed):

- 1. The evaluator will perform the efficacy evaluations including the EGSS, inflammatory and non-inflammatory lesion counts. The EGSS is performed prior to the lesion counting. Every effort should be made for the same qualified and validated evaluator to perform the efficacy evaluations at all visits from Baseline to Week 12 for the same subject.
- 2. For subjects who are applying study drug to truncal acne, the TSS will be performed. Note: lesion counts will not be performed for truncal acne.
- 3. The evaluator will perform the Cutaneous Safety and Tolerability Evaluations. For subjects who are applying study drug to truncal acne, then the Cutaneous Safety and Tolerability Evaluations will also be performed for these areas.
- 4. Record changes in any concomitant medications / therapies since the previous visit under Prior and Concomitant Medications or Therapies. Check for prior and concomitant medications / therapies as per Section 9.4.
- 5. Record any new AEs reported spontaneously by the subject or changes in any ongoing AEs.
- 6. Perform a urine pregnancy test for all females who are premenses and FOCBP. The urine pregnancy tests will be supplied by the CRO/designee.
- 7. The study coordinator or designee will collect/retrieve and weigh the used study drug pump (with the cap on) to the nearest 0.1 g. Assign the subject a new kit number (i.e., the number that was generated by the RTSM). Once a kit has been assigned to a subject, the kit should be pulled from pre-dispensing storage conditions, and kept in the secure drug storage area by an unblinded dispenser for approximately 10 to 15 minutes before

- dispensing to the subject. The new pump will be weighed (with the cap on) using a calibrated scale. Record the weight of the pump to the nearest 0.1 g.
- 8. The study diary calendar will be collected and reviewed for compliance. Any missed doses or deviations should be reported. A new study diary calendar will be dispensed.
- 9. Select Sites Only Obtain representative photographs of the face.
- 10. The study coordinator or designee will remind the subject of the proper technique for application of the study drug (Section 10.1.3). At this visit, the subject will apply the study drug at the study center under the direction of the study coordinator or designee to confirm proper technique. Any necessary retraining can be completed. The study drug should be applied **after** all clinical assessments. The study coordinator or designee will remind the subjects to apply the study drug once daily at home in the evening up to evening prior to Week 12 visit (study drug will not be applied in the evening after this study visit).
- 11. The study coordinator will instruct the subject to use a Sponsor/Investigator-approved, non-medicated sunscreen of at least SPF 15, and to wear protective clothing during the day (eg., a hat) if exposure cannot be avoided.
- 12. Schedule the next study visit at Week 8 (Day 56 ± 3 days). Remind the subject to not apply study drug on day of next study visit, prior to the clinic visit.

11.1.5 Visit 5: Week 8 (Day 56 ± 3 Days) Visit

The following procedures will be conducted at this visit (if a subject terminates early, all final visit [Week 12/Final Visit] procedures must be performed):

- 1. The evaluator will perform the efficacy evaluations including the EGSS, inflammatory and non-inflammatory lesion counts. The EGSS is performed prior to the lesion counting. Every effort should be made for the same qualified and validated evaluator to perform the efficacy evaluations at all visits from Baseline to Week 12 for the same subject.
- 2. For subjects who are applying study drug to truncal acne, the TSS will be performed. Note: lesion counts will not be performed for truncal acne.
- 3. The evaluator will perform the Cutaneous Safety and Tolerability Evaluations. For subjects who are applying study drug to truncal acne, then the Cutaneous Safety and Tolerability Evaluations will also be performed for these areas.
- 4. Record changes in any concomitant medications / therapies since the previous visit under Prior and Concomitant Medications or Therapies. Check for prior and concomitant medications / therapies as per Section 9.4.
- 5. Record any new AEs reported spontaneously by the subject or changes in any ongoing AEs.
- 6. Perform a urine pregnancy test for all females who are premenses and FOCBP. The urine pregnancy tests will be supplied by the CRO/designee.
- 7. The study coordinator or designee will collect/retrieve and weigh the used study drug pump (with the cap on) to the nearest 0.1 g. Assign the subject a new kit number (i.e., the number that was generated by the RTSM). Once a kit has been assigned to a subject, the

kit should be pulled from pre-dispensing storage conditions, and kept in the secure drug storage area by an unblinded dispenser for approximately 10 to 15 minutes before dispensing to the subject. The new pump will be weighed (with the cap on) using a calibrated scale. Record the weight of the pump to the nearest 0.1 g.

- 8. The study diary calendar will be collected and reviewed for compliance. Any missed doses or deviations should be reported. A new study diary calendar will be dispensed.
- 9. Select Sites Only Obtain representative photographs of the face.
- 10. The study coordinator or designee will remind the subject of the proper technique for application of the study drug (Section 10.1.3). At this visit, the subject will apply the study drug at the study center under the direction of the study coordinator or designee to confirm proper technique. Any necessary retraining can be completed. The study drug should be applied **after** all clinical assessments. The study coordinator or designee will remind the subjects to apply the study drug once daily at home in the evening up to evening prior to Week 12 study visit (study drug will not be applied in the evening after this study visit).
- 11. The study coordinator will instruct the subject to use a Sponsor/Investigator approved, non-medicated sunscreen of at least SPF 15, and to wear protective clothing during the day (eg, a hat) if exposure cannot be avoided.
- 12. Schedule the next study visit at Week 12 (Day 84 -3/+5 days). Remind the subject to not apply study drug on day of next study visit, prior to the clinic visit.

11.1.6 Visit 6: Week 12 (Day 84 -3/+5 Days) Visit – End of Study Visit

The following procedures will be conducted at this visit:

- 1. The Acne-QoL questionnaire will be completed by the subject and collected prior to any other study related procedures.
- 2. Perform an abbreviated physical examination, including measurements of weight and vital signs (blood pressure, heart rate, respiration rate, and oral temperature). Any abnormal physical examination findings will be recorded.
- 3. The evaluator will perform the efficacy evaluations including the EGSS, inflammatory and non-inflammatory lesion counts. The EGSS is performed prior to the lesion counting. Every effort should be made for the same qualified and validated evaluator to perform the efficacy evaluations at all visits from Baseline to Week 12 for the same subject.
- 4. For subjects who are applying study drug to truncal acne, the TSS will be performed. Note: lesion counts will not be performed for truncal acne.
- 5. The evaluator will perform the Cutaneous Safety and Tolerability Evaluations.
- 6. Record changes in any concomitant medications / therapies since the previous visit under Prior and Concomitant Medications or Therapies. Check for prior and concomitant medications / therapies as per Section 9.4.
- 7. Record any new AEs reported spontaneously by the subject or changes in any ongoing AEs.

40

8. The study diary calendar will be collected and reviewed for compliance. Any missed doses or deviations should be reported.

- 9. The study coordinator or designee will retrieve all study drug (pump[s]) from the subject and weigh the pump(s) using a calibrated scale. The weight of the pump(s) (with the cap on) should be recorded to the nearest 0.1 g.
- 10. Perform a urine pregnancy test for all females who are premenses and FOCBP. The urine pregnancy tests will be supplied by the CRO/designee.
- 11. Collect blood samples for routine laboratory analysis (CBC/Diff, serum chemistry, and serum pregnancy for all pre-menses females and FOCBP).
- 12. Select Sites Only Obtain representative photographs of the face.
- 13. Exit the subject from the study and complete the end of study eCRFs.

11.2 Evaluation of Efficacy

The determination of efficacy will be based on evaluator-blinded assessments of the signs and symptoms of acne vulgaris. Evaluators must be a board-certified/board-eligible dermatologist or have appropriate documented experience and training, and be present for formal study training and validation at the Investigator Meeting (and/or Site Initiation Visit), or obtain a waiver from the Sponsor based on experience (or through additional training organized by the Sponsor).

The EGSS assessments and lesion counts will be performed at each study visit. The EGSS assessments will be collected *before* the lesion counts. All subject assessments will be performed by a trained and validated evaluator. Every effort should be made to have the same evaluator assess the same subject at each visit. If this is not possible, the same evaluator should assess the subject at both the Baseline and Week 12 visits. If applicable, a separate TSS assessment and score will be collected and recorded for truncal acne at all study visits, starting at Baseline.

11.2.1 Evaluator's Global Severity Score (EGSS) and Truncal Severity Score (TSS)

The EGSS will be a static assessment that is independent of the baseline score. The investigator will make the assessment without referring to the baseline value. Every effort should be made for the same evaluator to perform each study assessment for the same study subject, for consistency in evaluations.

Subjects are eligible if they have acne vulgaris with a global severity of 3 (moderate) or 4 (severe) on the EGSS at the Baseline visit. The following scores will be used to describe the severity grade and subsequent score:

Table 4. Evaluator's Global Severity Score – Face

Score	Grade	Description
0	Clear	Normal, clear skin with no evidence of acne vulgaris
1	Almost Clear	Rare non-inflammatory lesions present, with rare noninflamed papules (papules must be resolving and may be hyperpigmented, though not pink-red)
2	Mild	Some non-inflammatory lesions are present, with few inflammatory lesions

CONFIDENTIAL

		(papules/pustules only; no nodulocystic lesions)
3	Moderate	Non-inflammatory lesions predominate, with multiple inflammatory lesions evident: several to many comedones and papules/pustules, and there may or may not be 1 nodulocystic lesion
4	Severe	Inflammatory lesions are more apparent, many comedones and papules/pustules, there may or may not be up to 2 nodulocystic lesions

For any subjects participating in the optional treatment of truncal acne (neck, upper chest, upper back and shoulders), Investigators will use the TSS scale below to grade truncal acne at each visit (starting at Baseline), recording the score as a separate score from the facial EGSS acne score on a separate TSS form.

Table 5. Truncal Severity Score (TSS) – Neck, Upper Chest, Upper Back & Shoulders

Score	Grade	Description
0	Clear	Normal, clear skin with no evidence of acne vulgaris
1	Almost Clear	Rare non-inflammatory lesions present, with rare noninflamed papules (papules must be resolving and may be hyperpigmented, though not pink-red)
2	Mild	Some non-inflammatory lesions are present, with few inflammatory lesions (papules/pustules only; no nodulocystic lesions)
3	Moderate	Non-inflammatory lesions predominate, with multiple inflammatory lesions evident: several to many comedones and papules/pustules, and there may or may not be 1 nodulocystic lesion
4	Severe	Inflammatory lesions are more apparent, many comedones and papules/pustules, there may or may not be up to 2 nodulocystic lesions

11.2.2 Lesion Counts

The facial area lesion counts will be taken from the subject's face (including the nose). The lesion count groups will be inflammatory and non-inflammatory. Facial inflammatory lesions (pustules, papules, and nodules) will be counted as follows: pustules and papules will be counted and recorded together, not separately; nodular lesions will be counted and recorded separately. Non-inflammatory lesions (open and closed comedones) will be counted and recorded together. The lesion counts will be collected at each visit and/or upon discontinuation. Note: lesions counts will not be conducted for truncal acne subjects. The following are definitions of each lesion type counted:

Inflammatory lesions are defined as follows:

Papule: An erythematous, raised, palpable lesion less than 5 mm in diameter

Pustule: An erythematous, raised, likely palpable lesion containing white exudate or pus less

than 5 mm

Nodule: A deep-seated, erythematous, firm lesion greater than 5 mm in diameter

Non-inflammatory lesions are defined as follows:

Open comedone (blackhead): A widely dilated sebaceous follicle plugged with darkly

pigmented sebum

Closed comedone (whitehead): A small, closed sebaceous follicle distended with sebum, with

a white appearance

11.2.3 Other Assessments

Photography

At select study centers, photographs of the face will be taken at Baseline and at Weeks 4, 8, and 12. Only subjects who provide written photographic consent for facial photographs will be included in photography. Note: photographs of truncal acne (if applicable) will not be conducted.

11.3 Evaluation of Safety

Safety assessments will be conducted at baseline and each subsequent study visit.

11.3.1 Cutaneous Safety Evaluations

Cutaneous safety will be evaluated through an assessment, conducted at the time of the study visit, of selected local signs (i.e., signs present at the study drug application site) that include the following: scaling, erythema, hypopigmentation, and hyperpigmentation. The evaluator will assess all cutaneous safety signs. For subjects treating (optional) truncal acne, cutaneous safety evaluations will also be conducted on this area throughout the course of the treatment/study, and recorded separately.

Cutaneous safety signs that result in the subject's requiring a concomitant therapy, interruption of treatment, or discontinuation from the study, will be reported as an AE.

Scaling:

0 – None No scaling

1 – Mild Barely perceptible, fine scales present on limited areas of the face

2 – Moderate Fine scale generalized to all areas of the face

3 – Severe Scaling and peeling of skin over all areas of the face

Ervthema:

0 – None No evidence of erythema present

1 – Mild Slight pink coloration

2 – Moderate Definite redness

3 – Severe Marked erythema, bright red to dusky dark red in color

Hypopigmentation:

0 – None No evidence

1 – Mild Slight, barely perceptible

2 – Moderate Definite, evident 3 – Severe Marked, prominent

Hyperpigmentation:

0 – None No evidence

1 – Mild Slight, barely perceptible

2 – Moderate Definite, evident3 – Severe Marked, prominent

11.3.2 Tolerability Evaluations

Tolerability will be evaluated through an assessment, at the time of the study visit, of selected local symptoms (i.e., symptoms present at the study drug application site) that include itching, burning, and stinging. The subject will self-assess all tolerability symptoms; the assessment will be based on an average over the period since the previous study visit.

For subjects treating (optional) truncal acne, tolerability evaluations will also be conducted on this area throughout the course of the treatment/study, and recorded separately.

Tolerability symptoms that result in the subject's requiring a concomitant therapy, interruption of treatment, or discontinuation from the study, will be reported as an AE.

Itching:

0 – None No itching

1- Mild Slight itching, not really bothersome

2 – Moderate Definite itching that is somewhat bothersome

3 – Severe Intense itching that may interrupt daily activities and/or sleep

Burning:

0 - None No burning

1 – Mild Slight burning sensation; not really bothersome

2 – Moderate Definite warm, burning sensation that is somewhat bothersome 3 – Severe Hot burning sensation that causes definite discomfort and may

interrupt daily activities and/or sleep

Stinging:

0 - None No stinging

1 – Mild Slight stinging sensation, not really bothersome

2 – Moderate Definite stinging sensation that is somewhat bothersome

3 – Severe Stinging sensation that causes definite discomfort and may interrupt daily

activities and/or sleep

11.3.3 Medical History and Abbreviated Physical Examination

A medical history will be taken at Screening, and confirmed and revised if needed, at Baseline. Medical histories having resolved 2 or more years before Baseline need not be collected unless considered relevant by the investigator.

An abbreviated physical examination including measurements of weight and vital signs (blood pressure, heart rate, respiration rate, and oral temperature) will be performed at Screening, Baseline and Week 12 (end of treatment/study); height will also be measured, but only at the

Screening visit. Any abnormal physical examination findings will be recorded and evaluated for AE reporting.

11.3.4 Laboratory Tests

Clinical laboratory analyses (CBC/Diff and serum chemistry) will be conducted on blood samples collected from subjects at Baseline and Week 12. All results will be reported, including results that are abnormal. Clinically significant results, in the opinion of the investigator, should be reported as AEs. If an AE should require laboratory testing, the results of the test must be obtained by the study center and filed in the subject's documentation.

For pre-menses females and FOCBP, a serum pregnancy test will be conducted at Baseline and Week 12.

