Blood samples will be collected from subjects at Baseline and Week 12 for CBC/Diff and serum chemistry. For all female subjects of childbearing potential (FOCBP), urine pregnancy testing will be performed at Screening, confirmed prior to randomization at Baseline, and then repeated at Weeks 2, 4, 8 and 12. Serum pregnancy test will also be conducted at Baseline and Week 12.

Subjects who terminate their study participation early will be asked to complete all Week 12 assessments, as appropriate. Subjects who discontinue from the study during the treatment period will not be replaced.

 Table 1.
 Study Design and Schedule of Assessments

PROCEDURES	VISIT 1 ^a Screening Visit (Day -35 to 0)	VISIT 2 Baseline Day 0	VISIT 3 Week 2 (Day 14±3 days)	VISIT 4 Week 4 (Day 28±3 days)	VISIT 5 Week 8 (Day 56 ± 3 days)	VISIT 6 ^b Week 12 (Day 84 -3/+5 days)
Informed Consent/Assent	X					
Obtain Subject Number from RTSM	X					
Demographics	X					
Medical History ^c	X	X				
Inclusion/Exclusion Criteria ^c	X	X				
Previous Therapies ^c	X	X				
Acne-QoL		X				X
Pregnancy Test (pre-menses and FOCBP) ^d	X	X	X	X	X	X
Abbreviated Physical Examination ^{c,e}	X	X				X
Vital Sign Measurements ^c	X	X				X
Safety Labs (CBC/Diff, serum chemistry)		X				X
EGSS	X	X	X	X	X	X
Lesion Counts	X	X	X	X	X	X
TSS (if applicable)		X	X	X	X	X
Photographs (select study centers only, face only)		X		X	X	X
Cutaneous Safety Evaluation ^f		X	X	X	X	X
Tolerability Evaluation ^f		X	X	X	X	X
Randomization in RTSM (obtain kit #)		X		X	X	
Administer Subject Instructions (see Appendix 17.1)		X				
Dispense Study Drug		X		X	X	
Weigh Study Drug		X	X	X	X	X
Study Drug Applied at Study Center		X	X	X	X	
Study Drug Collected				X	X	X
Subject Diary Calendar Dispensed		X	X	X	X	
Subject Compliance Reviewed / Diary Reviewed			X	X	X	X
Adverse Events	X	X	X	X	X	X
Concomitant & Prohibited Therapies/Medication Review	X	X	X	X	X	X
End of Study						X

^a If no washout is needed, Visits 1 and 2 may occur on the same day. If a washout is needed, Visit 2 must occur after the appropriate washout period.

Version 2.0, 2 March 2021 CONFIDENTIAL

^b All Week 12 procedures must be completed for all subjects who terminate early.

^cUpdate at Baseline visit prior to randomization.

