11.1.2 Visit 2: Baseline Visit (Day 0)

If a washout is not needed, this visit may occur on the same day as the Screening Visit (Visit 1). If a washout is needed, Visit 2 (Baseline) must occur after the appropriate washout period based on the criteria provided in Section 8.2.

The following procedures will be conducted at this visit:

- 1. The baseline Acne-QoL questionnaire will be completed by the subject and collected prior to conducting any other study-related procedures.
- 2. Verify that the subject continues to meet the applicable inclusion/exclusion criteria as outlined in Sections 8.1 and 8.2.
- 3. Record any changes in medical history since screening.
- 4. Record changes in any concomitant medications or therapies since the previous visit under Prior and Concomitant Medications or Therapies. Check for prior and concomitant medications / therapies as per Section 9.4.
- 5. Perform a urine pregnancy test for all females who are premenses and FOCBP. The urine pregnancy tests will be supplied by the CRO/designee.
- 6. Perform an abbreviated physical examination, including measurements of weight and vital signs (blood pressure, heart rate, respiration rate, and oral temperature). Any abnormal physical examination findings will be recorded.
- 7. The evaluator will perform the Baseline efficacy evaluations including an assessment based on the EGSS, and counts of inflammatory and non-inflammatory lesions. The EGSS is performed prior to the lesion counting. Every effort should be made for the same qualified, validated evaluator to perform the efficacy evaluations at all visits from Baseline to Week 12 for the same subject.
- 8. If the subject presents with truncal acne and agrees to have their study drug applied to these areas, then TSS will be performed from Baseline to Week 12. Note: lesion counts will not be performed for truncal acne.
- 9. The evaluator will perform the Cutaneous Safety and Tolerability Evaluations. If the subject presents with truncal acne and agrees to have their study drug applied to these areas, then the Cutaneous Safety and Tolerability Evaluations will also be performed for these areas.
- 10. Collect blood samples for routine laboratory analysis (CBC/Diff, serum chemistry, and serum pregnancy for pre-menses females and FOCBP).
- 11. Select Sites Only Obtain representative photographs of the face.
- 12. Assign the subject the appropriate kit number (this number will be generated from the RTSM).

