- 13. Once a kit has been assigned to a subject, the kit should be pulled from pre-dispensing storage conditions, and kept in the secure drug storage area by an unblinded dispenser for approximately 10 to 15 minutes before dispensing to the subject.

14. The study coordinator or designee will weigh a pump from the assigned kit and dispense it to the subject. The pump will be weighed (with the cap on) using a calibrated scale. Record the weight of the pump to the nearest 0.1 g. A study diary calendar will also be dispensed and the subject will be instructed to bring it to all subsequent visits.

- 15. The study coordinator or designee will instruct the subject on the proper application procedure for the study drug per Section 10.1.3, and will provide written subject use instructions to the subject (Appendix 17.1). For the first application, the subject will apply the study drug at the study center under the direction of the study coordinator or designee. The study drug should be applied after all clinical assessments. The study coordinator or designee will instruct the subjects to apply the study drug once daily at home at the same time of day, and will instruct the subject to use an investigator-approved, non-medicated sunscreen of at least SPF 15, and to wear protective clothing during the day (eg, a hat) if exposure cannot be avoided.
- 16. Record any AEs or changes in AEs since the screening visit and/or reported spontaneously by the subject.
- 17. Schedule the next study visit at Week 2 (Day 14 ± 3 days). Remind the subject not to apply study drug on day of next study visit.

NOTE: At the Baseline and Week 12 visits, serum pregnancy testing is **mandatory** for all pre-menses females and females of childbearing potential.

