12.2.1 Adverse Events

All AEs occurring during the study will be recorded and classified on the basis of Medical Dictionary for Regulatory Activities (MedDRA) terminology. Descriptions of AEs will include the date of onset, the date the AE ended, the severity of the AE, the relationship to study drug, the action taken regarding study drug usage, the action taken to treat the AE, and the outcome.

Treatment-emergent adverse events (TEAEs) are those events with an onset on or after the date of the first study drug application. All reported TEAEs will be summarized by the number of subjects reporting TEAEs, system organ class, preferred term, severity, seriousness, and relationship to study drug.

Adverse events will be summarized by treatment group and severity. Each subject will be counted only once within a system organ class or a preferred term by using the AEs with the highest severity within each category.

Adverse events will be summarized by treatment group and relationship to study drug. Each subject will be counted only once within a system organ class or a preferred term by using the AEs with the greatest relationship within each category.

The percentage of subjects reporting AEs will be summarized by treatment group for AEs occurring in at least 5% of subjects (in any treatment group). The percentage of subjects for each treatment group will be compared using a Fisher's Exact test.

All information pertaining to AEs noted during the study will be listed by subject, detailing the verbatim term given by the investigator, preferred term, system organ class, start date, stop date, severity, action taken, and drug relatedness. The AE onset will also be shown relative (in number of days) to the day of initial dose of the randomized study drug.

Serious adverse events will be tabulated by subject within treatment groups.

In addition, a list of subjects who discontinued from the study and a list of subjects who experienced SAEs will also be provided.

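### The date-only TEAE definition in Section 12.2.1 counts a pre-dose laboratory finding reported as an AE and dated Day 0 as treatment-emergent

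*Combined protocol and SAP*

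**What the plan says.** **Laboratory rule.** Section 11.3.4 says that the safety laboratory analyses "will be conducted on blood samples collected from subjects at Baseline and Week 12", and then: "Clinically significant results, in the opinion of the investigator, should be reported as AEs". The Baseline sample is not excepted. Section 11.4.2 also uses clinical significance as its filter for laboratory AEs, with no condition on change from Baseline.

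**AE definition.** Section 11.4.1 starts AE collection at consent and limits AEs to events that are new or worse during the trial. Neither 11.3.4 nor 11.4.2 repeats that limit for laboratory results.

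**Order of events on Day 0.** Table 1 marks safety laboratory tests at Baseline and Week 12 only. In Section 11.1.2, step 10 is "Collect blood samples for routine laboratory analysis", step 12 assigns the kit, and step 15 states "For the first application, the subject will apply the study drug at the study center".

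**TEAE rule.** Section 12.2.1 defines TEAEs as "those events with an onset on or after the date of the first study drug application". Section 11.4.2 lists onset and end dates for collection, but no onset time.

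**The concern.** A treatment-emergence rule should separate what was present before the first dose from what came after it. A rule based on date alone cannot do so on the day of first dosing. Here that day also carries the only pre-treatment laboratory sample, along with other Baseline assessments.

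With no Screening sample, the Day 0 result is the trial's first laboratory look at any existing abnormality. The protocol then directs sites to report clinically significant results as AEs. Findings that study drug cannot have caused may therefore enter the TEAE tables in every arm. That would raise the reported TEAE rate and pull between-arm ratios toward 1.

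**Working it through.** The plan states no figure on this point, so the check compares the rules and then sizes the effect under stated assumptions.

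**1. Does the rule capture a pre-dose finding?**

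- Sample date: Day 0 (Section 11.1.2, step 10).
- Date of first application: Day 0 (Section 11.1.2, step 15).
- Test in Section 12.2.1: onset date ≥ date of first application.
- Onset recorded as the sample date: 0 ≥ 0 is true, so the event is a TEAE.
- Onset recorded as a later result date: also true.
- Onset recorded before Day 0, or the finding entered only as medical history: not a TEAE.

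A rule based on date and time, or on start or worsening after the first application, would class the first two cases as not treatment-emergent.

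**2. Does another section prevent this?**

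- Section 11.4.1 would keep out an abnormality judged to pre-date the trial. Section 11.3.4 does not say so, and no earlier trial sample exists to show it.
- Screening may be up to 35 days before Baseline (Table 1). An abnormality that arises between consent and Day 0 is a valid AE under 11.4.1, yet it is still pre-dose. The TEAE rule misclassifies it if it is dated Day 0.
- Medical history is updated at step 3 of the Baseline visit, before the blood draw, and Table 1 footnote c places the update before randomization. Nothing directs sites to enter a Baseline laboratory finding there once the result is known.

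**3. How large could it be?**

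The documents give no rate of clinically significant Baseline results that would be reported as AEs and dated Day 0 or later. I assume 1% to 3% of subjects.

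- Per group of 220 (IDP-126, Epiduo Forte, or the combined vehicle groups): 220 × 0.01 = 2.2 and 220 × 0.03 = 6.6, so about 2 to 7 subjects.
- Section 12.2.1 threshold for comparing AEs, 5% in any group: 220 × 0.05 = 11 subjects.
- Synopsis threshold, 1% in either active group: 220 × 0.01 = 2.2, so 3 subjects.

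**4. What happens to a comparison?**

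For illustration, assume true post-dose rates of 3% and 1%, and add the same pre-dose rate *b* to both groups, in different subjects.

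| *b* | Rates shown | Ratio | Difference |
|---|---|---|---|
| 0% | 3% vs 1% | 3.0 | 2 points |
| 1% | 4% vs 2% | 2.0 | 2 points |
| 3% | 6% vs 4% | 1.5 | 2 points |

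The ratio falls and the risk difference does not change. Blood is drawn before the kit is assigned, so equal rates across groups are the right expectation.

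**The case against.** The strongest reply is that Section 11.4.1 governs. It names clinically significant laboratory abnormalities among AEs and requires them to be new or worse during the trial, so an abnormality already present at Baseline is not an AE. This narrows the problem but does not remove it. Sections 11.3.4 and 11.4.2 do not carry the limit, and the TEAE rule still misclassifies a valid AE that arose between consent and the first dose and is dated Day 0.

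The remaining objections mostly stand, and they limit the size of the point:

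- The result depends on how sites date onset. The documents do not say that the sample date is the onset date.
- Clinical significance is a narrow filter as illustrated in Section 11.4.2, and exclusion criterion 20 removes subjects with uncontrolled disease of safety concern. The affected group is probably small.
- The laboratory shift tables and change-from-Baseline summaries in Section 12.2.2 already account for Baseline status and are unaffected.
- Pre-dose findings can be recorded as not related to study drug, and listings show onset relative to first dose, so Day 0 events can be found.
- Under the 5% threshold in Section 12.2.1, 2 to 7 subjects alone would not bring a term into the Fisher comparison. Under the synopsis threshold of 1%, three subjects would.
- Section 12 announces a separate SAP. The text available contains no refinement of the TEAE definition, but one placed there could not be checked.

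A reader might also infer that abnormal Baseline examination findings follow the same route. That is weaker. Examinations and vital signs are also done at Screening, and Section 11.3.3 asks for findings to be evaluated for AE reporting, which leaves room for judgment. The examination case is at most secondary.

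**Conclusion.** The point holds in a limited form. As written, a pre-dose laboratory finding reported as an AE and dated Day 0 or later is a TEAE. This follows from the text of Sections 11.1.2, 11.3.4, 11.4.2 and 12.2.1, and Section 11.4.1 does not repair it.

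The likely effect is modest: about 2 to 7 of 220 subjects per large arm at an assumed 1% to 3%, with TEAE counts inflated and ratios diluted. No systematic bias between arms is expected, and the laboratory shift tables are not affected.

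Three stronger readings are tempting, and the documents do not support them:

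- *Every existing abnormality becomes a TEAE.* This requires the finding to be judged clinically significant, reported as an AE despite 11.4.1, and dated Day 0 or later.
- *About half of laboratory-derived TEAEs would be pre-dose, because there is one sample before and one after dosing.* This assumes that new Week 12 abnormalities are as common as existing Baseline ones, and no rate is given for either.
- *The comparison between arms is biased.* The sample precedes kit assignment, so the extra events should balance on average.

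The correction is still worth making, because the stated rule misclassifies pre-dose events and is cheap to change.

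**What to change.** **Section 12.2.1.** Define a TEAE as an event that starts or worsens after the first application of study drug. Add a before/after-first-dose flag, or an onset time, for events dated Day 0. Findings from assessments made before the application are then not treatment-emergent unless they later worsen.

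**Section 11.3.4.** Align the laboratory rule with Section 11.4.1. An abnormality judged pre-existing at Baseline is recorded as medical history, including when the result arrives after the visit. One judged to have arisen between consent and the first dose stays a reported AE, classed as not treatment-emergent. Moving all Baseline findings to medical history would not do, because it conflicts with AE collection from consent.

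Carry the same definition into the separate SAP.

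**Cost.** One eCRF field, a completion note, and a sentence or two in each section. No new samples or visits are needed, and Baseline results remain in the listings and shift tables.
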